2.1 Table 1: Schedule of Events

	Screening	(Up to 56 da	ays)		Day 1	Week 2 Day 15 +/- 3 days	Week 4 Day 29 +/-3 days	Week 5 Day 36 +/-3 days	Week 8 Day 57 +/- 3 days	Week 12 Day 85 /- 3 days	Week 16 Day 113 +/- 3 days	Week 17 Day 120 +/-3 days	Week 20 Day 141 +/-3 days	Week 30 Day 211 +/-7 days
Procedure	Visit 1 Screening Visit	Visit 2 Diary Run-In Visit	Diary Run-In Period (10-14 days)	MRI visit	Visit 3 Randomization Dose 1	Visit 4 Phone Visit	Visit 5 Dose 2	Visit 6	Visit 7 Dose 3	Visit 8 Dose 4	Visit 9 Dose 5	Visit 10	Visit 11 FU/EOT Visit*	Visit 12 FU Safety Phone visit**
Informed Consent	X													
Demography	X													
Medical History	X													
Concomitant Medication ^{1,2,3}	X	X			X	X	X		X	X	X		X	X
Eligibility Criteria ⁴	X	X		X	X									
Selection of Target Knee ⁵					X									
Randomization					X									
Radiographs ⁶	X												X	
MRI ⁷				X									X	
eDiary Review/Training ⁸		X			X	X	X	X	X	X	X	X		
Adverse Events	X	X			X	X	X	X	X	X	X	X	X	X
Average Daily NRS Pain (both knees)			•	-										
Average Daily NRS Pain (Target Knee only)					•								*	
Administer Study Drug					X		X		X	X	X			
48 h analgesic wash-out ¹	X	(X)			X		X	X	X	X	X	X	X	
WOPAIN NRS (both knees) ⁹	X	(X)												

CONFIDENTIAL

Clinical Trial Protocol

LEVI-04-21-02

Version

	Screening (Up to 56 days)					Week 2	Week 4	Week 5	Week 8	Week 12	Week 16	Week 17	Week 20	Week 30
						Day 15	Day 29	Day 36	Day 57	Day 85	Day 113	Day 120	Day 141	Day 211
						+/- 3 days	+/-3 days	+/-3 days	+/- 3 days	+/- 3 days	+/- 3 days	+/-3 days	+/-3 days	+/-7 days
Procedure	Visit 1	Visit 2	Diary	MRI	Visit 3	Visit 4	Visit 5	Visit 6	Visit 7	Visit 8	Visit 9	Visit 10	Visit 11	Visit 12
	Screening Visit	Diary Run-In Visit	Run-In Period (10-14 days)	visit	Randomization Dose 1	Telephone Visit	Dose 2		Dose 3	Dose 4	Dose 5		FU/EOT Visit*	FU Safety Phone visit*
WOMAC questionnaire					X			X				X		
(Target knee)														
StEPP					X			X				X		
PGA					X			X				X		
BCTQ	X								X				X	
SAS	X								X				X	
Physical Exam	X				X		X		X	X	X		X	
Musculoskeletal Exam					X		X		X	X	X		X	
Vital Signs	X				X		X		X	X	X		X	
ECG	X				X		X		X	X	X			
Rescue Medication ¹⁰		X			X		X	X	X	X	X	X	X	
Weight	X				X				X				X	
Height	X													
BMI ¹¹	X				X				X				X	
Blood Safety labs	X				X		X		X	X	X		X	
Serum hCG ¹²	X													
Blood Test for PK ¹³					X		X		X	X	X		X	
Blood Test for PD ¹⁴					X		X						X	
Anti-Drug Antibodies ¹⁴					X		X						X	
Urine Dipstick analysis ¹⁵					X		X		X	X	X			
Urine Dipstick hCG					X		X		X	X	X		X	

CONFIDENTIAL

Clinical Trial Protocol

LEVI-04-21-02

Version

^{*}All participants should complete Visit 11 and Visit 12. If a participant has discontinued trial early (prior to completion of Visit 10), the EOT/FU visit should be completed at 4 weeks (+/-3 days) of last IMP dose received and the Follow-up safety visit (phone visit) be scheduled at least 12 weeks following last IMP administration.

¹Participants are required to stop any analgesic medication at the start of the Diary Run-In Period and until completion of visit 11 FU/EOT visit. Rescue Medication will be provided (Paracetamol, max 4000 mg/day), but participants must be discouraged from taking it, particularly in the 48 hours prior to visits.

²Review of contraception use for WOCBP and male participants with female partners of childbearing potential.

³Review usage of illicit and recreational substances

⁴Ensure participant is eligible on all inclusion/exclusion criteria

⁵Selection of Target Knee after completion of the Diary Run-In Period and MRI of both knees has been read.

⁶Radiographs of both knee-, shoulder- and hip joints can be performed at any time prior to Visit 2 as long as they have been evaluated for eligibility prior to Visit 2

⁷MRI to be completed for both knees during Screening and reviewed for eligibility prior to selection of Target Knee at Visit 3. MRI of Target Knee only at study completion (FU/EOT visit)

⁸Ensure that the participant understands how to use the eDiary daily for completion of Average Daily NRS Pain score(s) and recording of any use of Rescue Medication. Accurate Pain Reporting (APR), Placebo Response Reduction (PRR) and Research Subject Responsibility (RSR) training to be completed at Visit 2 and Visit 3. Training modules to be repeated if indicated.

⁹WOMAC Pain subscale (WOPAIN NRS) for both knees to be completed during Screening prior to starting the Diary Run-In Period. The participant is required to abstain from taking analgesics in the 48-hours prior to completion or be treatment naïve. If not completed at Visit 1, WOPAIN NRS can be completed at Visit 2.

¹⁰Rescue Medication (Paracetamol) dispensation, and use of Rescue Medication accounted for.

¹¹BMI calculated automatically in EDC

¹²Serum hCG to be collected during Screening for WOCBP. If needed, safety labs can at all later timepoints include a Serum hCG.

¹³At IMP dosing visits PK samples are to be collected pre-dose and post-dose (following completion of IMP infusion, before leaving the clinic). At Visit 11/EOT the PK sample can be taken at any time of visit.

¹⁴ Samples for PD biomarkers and Anti-Drug Antibodies to be taken pre-dose at Visits 3, 5 and 11.

¹⁵ Urine dipstick analysis to be performed locally at site. If any clinically significant out-of-range values or indicated by symptoms, participant will be referred to primary care.

Version Version 3.0_07FEB2023

3 Background Information

3.1 Study Rationale

Symptomatic knee OA is a painful chronic joint disease estimated to affect approximately 45% of the population during a lifetime¹. Clinical manifestations include joint stiffness, swelling, crepitus, and limited mobility, but the hallmark symptom of OA is pain². Pain is the driving symptom leading patients to seek treatment and the symptom that most affects quality of life³. OA pain etiology, however, is complex, heterogenic, and yet to be fully understood⁴.

Among several available guidelines for management of knee OA pain The European Society for Clinical and Economic Aspects of Osteoporosis and Osteoarthritis (ESCEO)⁵ and Osteoarthritis Research Society International (OARSI)⁶, are consistent in the majority of their recommendations: Following core treatments (e.g. patient education and exercise programs), both the OARSI and ESCEO recommend the use of topical Non-Steroidal Anti-inflammatory Drugs (NSAIDs) and short-term use of paracetamol (acetaminophen) as first-line pharmaceutical management of knee OA pain. Patients with persistent pain are recommended oral NSAIDs, however, only to be used intermittently for the shortest period and at the lowest possible dose, due to their known adverse cardiovascular, hepatic, and renal risks. If such treatments are insufficient or not well tolerated, both guidelines recommend intraarticular corticosteroid injection or/and hyaluronic acid injections. Though highly efficient in the short term (2-4 weeks) intraarticular injections with corticosteroids are associated with osteoporosis, decreased efficiency when used long- term (over 6 weeks),⁷ and risk of accelerated cartilage loss⁸. As a last option, prior to recommending surgical intervention, guidelines recommend short-term treatment with opioids or treatment with Duloxetine, a serotonin–norepinephrine reuptake inhibitor (SNRI).

In conclusion treatment options for sufficient long-term OA pain management is limited and/or unsustainable, possibly leading clinicians to overprescribe drugs with serious and complicated long-term effects such as NSAIDs and opioids.

Despite numerous attempts in clinical drug development to provide a durable, safe, and effective treatment option, none have currently been successful. Targeted drug development of pain medication and further research on OA pain pathology is therefore warranted.

3.2 Scientific Rationale and Role of Target in the Disease

LEVI-04's primary mode of action is inhibition of the activity of the Neurotrophins; Nerve Growth Factor (NGF) and Neurotrophin-3 (NT3) to reduce pain.

NGF is an important mediator of pain associated with OA⁹. Monoclonal antibodies against NGF showed efficacy in treating chronic pain due to OA in phase III clinical trials^{10,11}. However, risk of Rapidly Progressing Osteoarthritis (RPOA)¹² and adverse effects on the sympathetic nervous system¹³ raised concerns regarding their safety.

LEVI-04 is a fusion protein and thus has a different antagonist profile to anti-NGF antibodies and differs on several points:

Version

Version 3.0 07FEB2023

- Unlike anti-NGF antibodies that require plasma concentrations ~1000-fold the primary affinity to demonstrate efficacy in clinical studies¹⁰, LEVI-04 is efficacious in preclinical models of OA at concentrations of its potency for inhibition of NGF activity.
- LEVI-04 exhibits a more gradual inhibition of NGF-induced activity compared with anti-NGF antibody mediated inhibition.
- Multiple preclinical studies, including comparative histopathology and neuropathological
 evaluation studies of LEVI-04 and anti-NGF antibodies, have been performed specifically to
 address any safety concerns (See IB for full overview). These studies confirmed the detrimental
 effects of anti-NGF antibodies, but found no evidence of such effects of LEVI-04 at therapeutic
 doses.

Together, this indicates LEVI-04 to not be associated with the known risk of RPOA associated with anti-NGF antibodies. Conversely, treatment with LEVI-04 was found to be associated with improvements in the histopathological assessments compared to the control animals, which could indicate a beneficial disease-modifying effect of LEVI-04. These preclinical findings support the investigation of LEVI-04 as a novel drug for the treatment of OA.

For a full description of the modalities of LEVI-04 and study references, see Description of the Investigational Medical Product (Section 6.1.1) and Investigators Brochure (IB).

3.3 Non-Clinical and Clinical Data

3.3.1 Non-Clinical data

The potential for toxicity of LEVI-04 has been evaluated in preliminary studies and formal toxicology studies. In 4-week, repeat-dose toxicity studies (cynomolgus monkeys and Han Wistar rats), LEVI-04 was well tolerated and no overt adverse toxicological effects were observed.

- LEVI-04 was well tolerated in rats at doses of 10, and 15 mg/kg. From this, the maximum tolerated dose is considered to be above 15 mg/kg.
- LEVI-04 was well tolerated in cynomolgus monkeys at all doses tested. From this study the maximum tolerated dose is considered to be above the 100 mg/kg dose.
- There were no adverse histopathological findings reported in the 4-week rat or cynomolgus monkey studies.
- In the rat study, non-adverse findings were limited to an increased incidence of wounding in the head and neck area in all doses tested. This effect was reversed during the treatment free period.
- In the cynomolgus monkey study, non-adverse neuropathological findings were described in the 30 and 100 mg/kg dose groups none of which were statistically significant (p>0.05) to those observed in corresponding control animals administered placebo.

Version Version 3.0 07FEB2023

• The No Observed Adverse Effect Level (NOAEL) for LEVI-04 in the Han Wistar rat and Cynomolgus monkey was 30 and 100 mg/kg weekly, respectively; the highest dose tested in each study. This correlated with C_{max} values of 1230000 and 1150000 ng/mL in male and female rats, respectively: and 3760000 and 4060000 ng/mL in the male and female monkeys, respectively. The human equivalent doses are 4.8 and 32.3 mg/kg for the NOAEL rat and monkey doses, respectively.

In a 26-week biweekly repeat dose (up to 30 mg/kg/dose) toxicology study in cynomolgus monkeys no relevant findings were made. There were no test related effects on organ weight and no gross nor microscopic findings.

3.3.2.1 Safety and tolerability

LEVI-04 was well tolerated. There were no deaths, non-fatal Serious Adverse Events (SAEs), or AEs leading to participant withdrawal from treatment during the study. All Treatment-Emergent Adverse Events (TEAEs) were mild or moderate in severity. There were no findings of clinically significant physical, neurological or local tolerability, nor significant changes in vital signs, safety ECGs or laboratory variables. LEVI-04 did not elicit an immunogenic response in any participant or cohort. Positive Assays for the Detection of Anti-drugs Antibodies (ADA) to LEVI-04 were detected in one HV; however, those ADAs were present already prior to dosing.

Version

Version 3.0 07FEB2023

3.3.2.1.1 Healthy Volunteer (HV) cohorts

In the HV Cohort (Cohorts 1–3 and 8), 53.6% reported at least 1 TEAE, only 1 of which (mild anxiety after 3.0 mg/kg LEVI-04) was considered by Investigator to be related to treatment. There was no evidence of a dose-related effect of LEVI-04 on the incidence of TEAEs in HV.

- The two must frequently reported System Organ Classes (SOCs) of the TEAEs were 'Infections and infestations', and 'Nervous system disorders' with 8 reported TEAEs in each class (7 and 6 participants, respectively).
- The most frequently reported TEAEs in HV cohorts were Headache, reported in 2 participants after Placebo, n=3 after 0.01 mg/kg LEVI-04, and n=1 after 3.0 mg/kg LEVI-04)
- All other TEAEs were reported by only one or two participants each, with no correlation to dose.
- Symptoms of autonomic dysfunction assessed by the Survey of Autonomic Symptoms (SAS) questionnaire occurred in 25.0% of HV on at least one occasion before or after dosing. There was no evidence of a dose-related effect of LEVI-04. One participant before 0.003 mg/kg LEVI-04, One participant before 3.0 mg/kg LEVI-04, Two participants before and after 0.01 mg/kg LEVI-04, Two participants before and after 0.03 mg/kg LEVI-04, One participant after Placebo.

The overall objective of this study is to evaluate the efficacy and safety of LEVI-04 compared to placebo in patients with knee OA. The Primary and Secondary objectives with corresponding endpoints and timeframes are included in following table.

4.1 Table 2: Objectives and mapped Endpoints

Objective(s)	Endpoint(s)							
Primary								
To evaluate the efficacy of LEVI-04 (multiple doses) compared to placebo in reducing pain due to knee OA.	Change in WOMAC pain subscale from Randomization (Visit 3) to Visit 10 (week 17)							
Secondary								
To evaluate the efficacy of LEVI-04 (multiple doses) compared to placebo in improving physical function.	Change in WOMAC Physical function subscale from Randomization (Visit 3) to Visit 6 (week 5) and Visit 10 (week 17).							
	Change in Staircase Evoked Pain Procedure (StEPP) from Randomization (Visit 3) to Visit 6 (week 5) and Visit 10 (week 17)							
To evaluate the efficacy of LEVI-04 (multiple doses) compared to placebo in improving joint stiffness.	Change in WOMAC Stiffness subscale from Randomization (Visit 3) to Visit 6 (week 5) and Visit 10 (week 17)							
To evaluate the efficacy of LEVI-04 (multiple doses) compared to placebo in Patient Global Assessment (PGA)	Change in PGA from Visit 6 (week 5) to Visit 10 (week 17)							

Version

Objective(s)	Endpoint(s)					
	Change in WOMAC Pain subscale from Randomization (Visit 3) to Visit 6 (week 5)					
To evaluate the proportion of responders based on various levels of reduced pain in participants receiving LEVI-04 (multiple doses) compared to	Proportion of participants achieving 30% and 50% reduction in WOMAC Pain subscale at week 5 and week 17 using a cumulative distribution function					
placebo	Change in average weekly NRS Pain score from Baseline to Visit 6 (week 5) and Visit 10 (week 17)					
	Area under the curve of Average Daily NRS Pain from Baseline to Visit 11 (week 20)					
To evaluate rescue medication use in the LEVI-04 group (multiple doses) compared to placebo.	Rescue Medication usage during the trial					
Exploratory						
To evaluate the efficacy of LEVI-04 compared to placebo in time to onset of pain relief	Time from Randomization to a decrease in average weekly NRS pain of 30% from Baseline NRS Pain score.					
To explore associations between	Associations of imaging biomarkers and pain severity at Randomization (Visit 3) to Visit 11 (week 20)					
imaging biomarkers and pain severity	Correlations between pain variability during screening and major efficacy endpoints					
To explore associations of biomarkers of the neurotrophin signaling pathway and pain severity	Change from Baseline in blood biomarkers and associations with clinical outcomes					
Safety						
To evaluate the overall safety of LEVI-04 compared to placebo	AEs between treatment arms (Count and Severity)					

Version

Version 3.0_07FEB2023

Objective(s)	Endpoint(s)
To evaluate the safety of LEVI-04 compared to placebo in relation to the peripheral nervous system	Peripheral Nervous System AEs between treatment arms (Count and Severity)
To evaluate the safety of LEVI-04 compared to placebo in relation to joint safety.	Incidences of Joint Events and subtypes of Joint Events. Events include: Osteonecrosis Destructive Arthropathy, including RPOA type 2 Changes in signs of inflammation on Magnetic resonance imaging (MRI) of the Target Knee, Subchondral insufficiency fracture Rapid loss of JSW by 2 mm within 12 months or loss of 50% of JSW if less than 2 mm at baseline. This is also called RPOA type 1 Any other incidence of joint events such as acute fracture, bone marrow infiltration, etc.

[figure not shown]
5 Investigational Plan

5.1 Overall Trial Design and Plan

This is a Multiple Arm, Multicenter, Prospective, Randomized, Double-blind, Placebo-controlled, Phase 2a study of LEVI-04 intravenous infusion for the treatment of knee osteoarthritis (OA). The purpose of the trial is to evaluate the efficacy, safety, and tolerability of five monthly infusions of LEVI-04 as compared to placebo in participants with radiographic and symptomatic knee OA. Eligible participants will be randomized to one of the four treatment arms: 0.3 mg/kg LEVI-04, 1.0 mg/kg LEVI-04, 2.0 mg/kg LEVI-04 or saline vehicle control (placebo) in a 1:1:1:1 ratio (Figure 1). All participants will receive five intravenous IMP infusions 4 weeks apart, i.e. at Randomization (Day 1), Visit 5 (week 4), Visit 7 (week 8), Visit 8 (week 12) and Visit 9 (week 16) with assessments and procedures as per Schedule of Events A Follow-up/End-of-Trial (FU/EOT) visit (Visit 11) and Follow-up Safety Phone Visit (Visit 12) will take place at week 20 and week 30, respectively.

Version Version 3.0 07FEB2023

5.1.1 Figure 1: Study Schema

5.2 Discussion of Trial Design

The overall trial design is considered an appropriate study design for Phase 2 drug development and consistent with current regulatory guidance. The primary goal of the study is to establish proof of concept of the biologic activity of LEVI-04 leading to reduction in pain from knee OA compared to placebo. The trial is designed to add to the LEVI-04 safety data collected in the Phase 1 trial (Clinical Trials.gov: NCT03227796, See IB) and establish the most suitable dose for a Phase 3 trial. The Primary endpoint is change in WOMAC pain subscale score from Randomization (Visit 3) to week 17 (Visit 10). WOMAC pain subscale is a Food and Drug Administration (FDA) recommended clinical trial efficacy endpoint for OA and considered a reliable, validated outcome measure^{14,15}. The study duration of 30 weeks which includes 14 weeks to Follow-up Safety Phone Visit 12 from last dose administered, and is considered sufficient to meet study objectives and ensure sufficient oversight of participant safety and follow-up of adverse events. Participants that discontinue trial early will be followed up at least 12 week following last administered dose of IMP. Radiographs of major joints bilaterally (knee-, hip-, and shoulder joints) and MRI of both knees during Screening are included to determine eligibility. Only Target Knee will have MRI completed at FU/EOT visit (week 20). Safety assessments throughout the trial include Physical examination, Vital signs, Clinical laboratory values, ECG, and AEs.

5.2.1 Selection of Trial Population

Only individuals meeting all Inclusion Criteria and no Exclusion Criteria may be enrolled into the trial as participants. Prospective approval of protocol deviations to recruitment and enrollment criteria, also known as protocol waivers or exemptions, are not permitted.

Version

Version 3.0_07FEB2023

Prior to performing any trial assessments not part of the participant's routine medical care, the Investigator will ensure that the participant or the participant's legal representative has provided written ICF.

5.2.2 Inclusion Criteria

- 1. Signed ICF
- 2. Male or female participants between ≥40 and ≤80 years of age
- 3. BMI ≤40 kg/m2
- 4. The ability, in the opinion of the investigator, to utilize the eDiary device provided and comply with study requirements
- 5. History of knee pain on most days for at least 3 months prior to Screening
- 6. Confirmation of OA of the Target knee
 - a. Radiographs of both knees with a Posterior-Anterior, Fixed-flexion view taken during the Screening Period
 - b. American College of Rheumatology (ACR) clinical and radiographic diagnostic criteria
- 7. Evidence of Target knee OA with a KL grade ≥2, determined through central reading
- 8. Target Knee must have a score of ≥20 out of 50 on the WOMAC NRS 3.1 pain subscale during Screening and at Randomization
- 9. The Baseline NRS Pain score will be derived from the last seven days of the Diary Run-In Period and must meet following criteria:
 - a. Completion of Average Daily NRS Pain score on at least 6 of the 7 days
 - b. Mean Average Daily NRS Pain score must be ≥4.0 and ≤9.0
 - c. Mean Average Daily NRS Pain variability must be ≤1.5
- 10. If female and not of childbearing potential defined as post-menopausal for at least 1 year, or surgically sterile (bilateral tubal ligation, bilateral oophorectomy, or hysterectomy), or practicing an agreed upon highly effective method of birth control throughout the study period and at least 3 months after last dosing of IMP
- 11. If male and sexually active with partner of childbearing potential, willing to agree to practice a highly effective method of contraception from Visit 2 and at least 3 months after Visit 11 (week 20)

Version

Version 3.0 07FEB2023

- 12. Willing to withdraw from any medication for OA including, but not limited to, Opioids (including semisynthetic opioids), Non-Steroidal Anti-inflammatories (NSAIDs), COX-2 inhibitors, Topical medication, and Serotonin and Noradrenaline Reuptake Inhibitors (SNRIs e.g Duloxetine)
- 13. Participant agrees to take only the allowed Rescue Medications from the start of the Diary Run-In Period through study completion (FU/EOT visit 11) (maximum 4000 mg paracetamol per day)

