	 Signed ICF Male or female participants between ≥40 and ≤80 years of age BMI ≤40 kg/m2 The ability, in the opinion of the investigator, to utilize the eDiary device provided and comply with study requirements History of knee pain on most days for at least 3 months prior to Screening Confirmation of OA of the Target knee Radiographs of both knees with a Posterior-Anterior, Fixed-flexion view taken during the Screening Period
	b. American College of Rheumatology (ACR) clinical and radiographic diagnostic criteria

Version

Version 3.0 07FEB2023

- 7. Evidence of Target knee OA with a KL grade ≥2, determined through central reading
- 8. Target Knee must have a score of ≥20 out of 50 on the WOMAC NRS 3.1 pain subscale during Screening and at Randomization
- 9. The Baseline NRS Pain score will be derived from the last seven days of the Diary Run-In Period and must meet following criteria:
 - a. Completion of Average Daily NRS Pain score on at least 6 of the 7 days
 - b. Mean Average Daily NRS Pain score must be ≥4.0 and ≤9.0
 - c. Mean Average Daily NRS Pain variability must be ≤1.5
- 10. If female and not of childbearing potential defined as post-menopausal for at least 1 year, or surgically sterile (bilateral tubal ligation, bilateral oophorectomy, or hysterectomy), or practicing an agreed upon highly effective method of birth control throughout the study period and at least 3 months after last dosing of IMP
- 11. If male and sexually active with partner of childbearing potential, willing to agree to practice a highly effective method of contraception from Visit 2 and at least 3 months after Visit 11 (week 20)
- 12. Willing to withdraw from any medication for OA including, but not limited to, Opioids (including semisynthetic opioids), Non-Steroidal Anti-inflammatories (NSAIDs), COX-2 inhibitors, Topical medication, and Serotonin and Noradrenaline Reuptake Inhibitors (SNRIs e.g Duloxetine)
- 13. Participant agrees to take only the allowed Rescue Medications from the start of the Diary Run-In Period through study completion (FU/EOT visit 11) (maximum 4000 mg paracetamol per day)

Exclusion criteria:

- 1. Presence of OA of other major joints (including but not limited to nontarget knee) that could interfere with assessment of pain due to OA of the target knee, in the opinion of the investigator.

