14.1 Appendix I: Contraceptive Guidance and Woman of Childbearing Potential

Definitions:

Woman of Childbearing Potential (WOCBP)

A woman is considered fertile following menarche and until becoming post-menopausal unless permanently sterile. Permanent sterilization methods include hysterectomy, bilateral salpingectomy, and bilateral oophorectomy.

Women in the following categories are not considered WOCBP

- 1. Premenopausal female with 1 of the following:
 - Documented hysterectomy
 - Documented bilateral salpingectomy
 - o Documented bilateral oophorectomy

Note: Documentation can come from the site personnel's: review of participant's medical records, medical examination, or medical history interview.

2. Premenarchal

3. Postmenopausal female

- Females who are postmenopausal (age-related amenorrhea ≥ 12 consecutive months and/or increased follicle-stimulating hormone [FSH] > 40 mIU/mL), or who have undergone hysterectomy or bilateral oophorectomy are exempt from pregnancy testing.
- Females on HRT and whose menopausal status is in doubt will be required to use one of the non-hormonal highly effective contraception methods if they wish to continue their HRT during the study. Otherwise, they must discontinue HRT to allow confirmation of postmenopausal status before study enrollment.

Version Version 3.0 07FEB2023

Highly Effective Contraceptive Methods That Are User Dependent

Failure rate of <1% per year when used consistently and correctly^a.

- Combined (estrogen- and progestogen-containing) hormonal contraception associated with inhibition of ovulation^b:
 - oral
 - · intravaginal
 - transdermal
- Progestogen-only hormonal contraception associated with inhibition of ovulation^b
 - oral
 - injectable

Highly Effective Methods That Are User Independent

- Implantable progestogen-only hormonal contraception associated with inhibition of ovulation^b
- Intrauterine device (IUD)
- Intrauterine hormone-releasing system (IUS)
- Bilateral tubal occlusion
- Vasectomized partner (A vasectomized partner is a highly effective contraception method provided that the partner is the sole male sexual partner of the WOCBP and the absence of sperm has been confirmed. If not, an additional highly effective method of contraception should be used).

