- Sexual abstinence (Sexual abstinence is considered a highly effective method only if defined as refraining from heterosexual intercourse during the entire period of risk associated with the study drug. The reliability of sexual abstinence needs to be evaluated in relation to the duration of the study and the preferred and usual lifestyle of the participant.)
- a) Typical use failure rates may differ from those when used consistently and correctly. Use should be consistent with local regulations regarding the use of contraceptive methods for participating in clinical studies.
- b) Hormonal contraception may be susceptible to interaction with the study drug, which may reduce the efficacy of the contraceptive method. In this case two highly effective methods of contraception should be utilized during the treatment period and for at least 90 days after the last dose of study treatment

Version Version 3.0 07FEB2023

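### Appendix I lets a raised FSH alone exempt a woman from pregnancy testing, while inclusion criterion 10 still treats her as possibly fertile

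*Protocol*

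**What the plan says.** **Criterion 10** (Protocol 5.2.2, repeated in the synopsis) has two routes for women. The first is to be "not of childbearing potential defined as post-menopausal for at least 1 year, or surgically sterile (bilateral tubal ligation, bilateral oophorectomy, or hysterectomy"). The second is "practicing an agreed upon highly effective method of birth control throughout the study period and at least 3 months after last dosing of IMP". FSH appears in neither.

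**Appendix I** (Protocol 14.1) defines a woman of childbearing potential (WOCBP) and lists who is not one. Postmenopausal women are on that list. The definition starts with age-related amenorrhea of 12 months or more and continues "and/or increased follicle-stimulating hormone [FSH] > 40 mIU/mL), or who have undergone hysterectomy or bilateral oophorectomy are exempt from pregnancy testing". The *and/or* makes a raised FSH sufficient without the amenorrhea, and the testing exemption is in the same sentence.

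**Which text sites use.** At Visit 1, Section 8.2.1 tells the site to review whether the participant is a WOCBP and points to Appendix I. The synopsis does the same in its Visit 1 medication review. Sections 7.10.1.1, 7.10.2 and 8 give routine hCG tests to WOCBP.

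**Surgery.** Criterion 10 counts tubal ligation as sterility and does not name salpingectomy. Appendix I states "Permanent sterilization methods include hysterectomy, bilateral salpingectomy, and bilateral oophorectomy" and places "Bilateral tubal occlusion" among the contraceptive methods.

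**The concern.** Two parts of one protocol classify the same woman differently, and she gets the less protective answer where it matters. For contraception she is treated as possibly fertile. For pregnancy testing she is treated as not fertile.

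Two safety rules depend on finding a pregnancy: exclusion criterion 22, which bars pregnant women, and Section 9.5, which requires trial medication to stop at once if a participant becomes pregnant. Contraception during the trial does nothing about a pregnancy already present at screening. Testing on suspicion is a weak substitute in a woman near menopause, because a missed period tells her little when her periods are already irregular.

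**Working it through.** No plan figure is in dispute, so the check sets the texts side by side for one woman.

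**The case.** She is 40 or older (criterion 2 sets the lower limit at 40), not on hormone replacement therapy (HRT) and not surgically sterile. She has a recently documented FSH above 40 mIU/mL and fewer than 12 months of amenorrhea.

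| Question | Text that decides it | Answer |
|---|---|---|
| Is she at least 1 year post-menopausal? | Criterion 10 | No |
| Must she use highly effective contraception? | Criterion 10 | Yes |
| Is she a WOCBP? | Appendix I, cited at Visit 1 | No, on FSH alone |
| Does she have routine hCG tests? | Appendix I exemption; Sections 7.10 and 8 | No |

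**Tests she misses.** Table 1 schedules serum hCG at Visit 1 and urine hCG at Visits 3, 5, 7, 8, 9 and 11, so 1 + 6 = 7 tests. The five doses are given at Visits 3, 5, 7, 8 and 9. She is exempt from the screening test, the five tests on dosing days and the one at Visit 11: 1 + 5 + 1 = 7.

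**Does other text close the gap?**

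- The HRT paragraph in Appendix I requires women on HRT whose status is in doubt to use a non-hormonal method if they wish to continue HRT; otherwise "they must discontinue HRT to allow confirmation of postmenopausal status before study enrollment". It does not reach a woman who is not on HRT.
- Table 1 footnote 12 and Section 7.10.1.1 allow serum hCG later if needed. Someone must first suspect pregnancy.
- Section 5.2.1 forbids eligibility waivers. That holds her to contraception but gives her no test.

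**How often could this arise?** FSH is not in the laboratory table in Section 7.10.1.1, so the value would have to come from outside records. The documents do not give the number of such women.

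**The case against.** The strongest reply is that the conflict is narrow. Criterion 10 does not define post-menopausal, so a woman whose FSH was documented above 40 mIU/mL a year or more ago may satisfy both texts. No trial procedure measures FSH, so none creates the case. The woman who is left must still use highly effective contraception, and can be tested at any later visit if there is reason. All of this stands and limits the size of the point. It does not remove the contradiction for a recently raised FSH.

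A reader might infer more in two places, and the documents do not support it.

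*That the surgical lists leave women untested or unsafe.* Visit 1 uses Appendix I to decide WOCBP status. Under it, a woman with tubal ligation is a WOCBP using a listed method, so she is eligible and tested. A woman with documented bilateral salpingectomy is not a WOCBP, so Sections 7.10 and 8 already leave her untested, with no loss of safety. Read literally, criterion 10 asks her for a contraceptive method, which is only over-cautious.

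*That the protocol contains competing test schedules.* The urine hCG row in Table 1 and the synopsis lines for Visits 1 and 9 are not limited to WOCBP. But the Table 1 row is not limited to women either, so it is a row label and not a rule. The synopsis lines are shorthand. Footnote 12 to Table 1 and Sections 7.10.1.1, 7.10.2 and 8 supply the WOCBP limit.

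**Conclusion.** The inconsistency is real and minor. Followed as written, Appendix I removes all routine pregnancy testing from a woman whom criterion 10 regards as possibly fertile, and she could receive five doses without an hCG test.

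The conclusion rests on two readings: that *and/or* carries its ordinary meaning, so FSH alone is enough, and that sites use Appendix I to decide WOCBP status, as Section 8.2.1 directs. The affected group is women with a recently raised FSH and under 12 months of amenorrhea. That it is small is a judgement, based on FSH not being a trial test. The primary and other efficacy analyses are unaffected.

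**What to change.** 1. In Appendix I, replace the postmenopausal definition with: *age-related amenorrhea of at least 12 consecutive months; FSH > 40 mIU/mL may support this but is not sufficient alone*.
2. In criterion 10 (Section 5.2.2 and synopsis), refer to Appendix I in place of a second definition, for example: *female and either not a WOCBP as defined in Appendix I, or using a highly effective method listed there during the study and for 3 months or more after the last dose*.

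The woman with raised FSH alone then uses contraception and has all seven tests. The second change also removes the differences on tubal ligation and salpingectomy. That is a tidy-up, with no separate safety claim.

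The cost is wording in an amendment (criterion 10 in two places and one definition in Appendix I) and at most seven hCG tests for each reclassified woman, at visits already scheduled.
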